3.2.3.3 Peripheral blood eosinophil and neutrophil counts

Absolute peripheral blood eosinophil counts and neutrophil counts are assessed by a central laboratory as a part of safety haematology testing according to the visit schedule defined in Tables 1 and 2 of the CSP.

Absolute eosinophil counts and absolute neutrophil counts along with their absolute changes from baseline, and percent changes from baseline for each post-baseline visit will be calculated as defined in Section 3.1.2 and Section 3.1.3, using conventional units (cells/ μ L).

3.2.3.4 Change from baseline in post-BD FEV₁ (L) at Week 52

Change from baseline in post-BD FEV₁ (L) at Week 52 will be another exploratory outcome variable and it will be derived similarly to pre-dose/pre-BD FEV₁ (L) in Section 3.2.2.5.

3.2.3.5 Exacerbations of Chronic Pulmonary Disease Tool– EXACT-PRO and E-RS™: COPD

The EXACT-PRO is a 14-item PRO instrument developed to assess the frequency, severity and duration of COPD exacerbations ([Jones et al 2011](#), [Leidy et al 2011](#)). The instrument was developed for daily, at home, administration using a handheld electronic device. Respondents are instructed to complete the eDiary each evening just prior to bedtime and to answer the questions while considering their experiences “today” up to Week 52. The daily EXACT-PRO total score has a range of 0-100 with higher scores indicative of greater severity. Total score changes are used to identify the onset and recovery from an EXACT-PRO defined exacerbation event. In identifying event onset and recovery, the EXACT-PRO can provide information on event frequency and duration as event severity.

The number, average duration, and severity of EXACT-PRO defined events will be evaluated. EXACT-PRO daily total scores will be calculated according to the developer approved scoring algorithm. The total score will be used to identify event onset and recovery as well as the magnitude (severity) of the event. The baseline total score will be the mean score within subject over the 7 days prior to randomisation. A minimum of 4 days of data is required for calculating the baseline total score. To allow for improvement or deterioration in disease state over the course of the trial, the baseline total score will be reset every 4 weeks in the absence of an EXACT-PRO defined event. Event frequency is calculated by comparing the baseline with daily total scores. An increase in EXACT-PRO total score ≥ 9 for 3 days or ≥ 12 for 2 days indicate an event has occurred. Calculating event duration requires identification of the following 5 parameters: 1) onset; 2) 3-day rolling average; 3) maximum observed value; 4) threshold for improvement; and 5) recovery. The severity of an event is indicated by the worst (highest) EXACT-PRO total score during an event. Complete details concerning variable calculation are provided in the scoring manual ([Evidera, Inc. 2014](#)).

For the production of summary statistics, the annual EXACT-PRO defined exacerbation rate in each treatment group will be calculated using the same time-based approach as specified in Section 3.2.1.

The E-RS: COPD is an 11-item PRO developed to evaluate the severity of respiratory symptoms of COPD ([Sexton et al 2010](#), [Sexton et al 2011](#)). The E-RS: COPD is a subset of items from the EXACT-PRO. The E-RS: COPD was designed to be captured as part of the daily EXACT-PRO assessment. Summation of E-RS: COPD item responses produces a total score ranging from 0 to 40, with higher scores indicating greater severity. In addition to the total score, symptom domain scores can be calculated for breathlessness (5 items; score range: 0–17), cough and sputum (3 items; score range: 0–11) and chest symptoms (3 items; score range: 0–12) by summing the responses of items within a respective domain. As with the total score, higher domain scores indicate greater severity.

Individual daily E-RS: COPD total and domain scores will be calculated and summarised as biweekly (14 days) means, derived by the following rules:

The biweekly mean is calculated as the sum of all non-missing daily measures/scores over 14 sequential days divided by the number of non-missing daily measures/scores. If more than 7 -daily measures/scores (>50%) within that period are missing, then the mean daily measure/score for that period is set to missing.

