7.1.1 Procedures for Discontinuation of Study Treatment

Subjects are free to discontinue IP or withdraw from the study at any time without prejudice to further treatment. Discontinuing study treatment is not the same as study withdrawal. In the case of early study withdrawal, the EOT visit should be completed immediately. Subjects who do not wish to have any follow-up contacts as detailed below, will be withdrawn from the study. Procedures to follow for study withdrawal are detailed below in Section 7.3. All withdrawn subjects must return the eDiary device at the EOT visit (and at IPD visit for subjects choosing option 3 below). If the subject decides to withdraw consent, then the reason for this must be recorded separately in the eCRF.

A subject that decides to discontinue IP should always be asked about the reason(s) and the presence of any adverse events. The reason for discontinuing treatment and the date of last IP administration should be recorded in the eCRF. Subjects permanently discontinuing IP administration should be given locally available SoC therapy, at the discretion of the Investigator. However, treatment with marketed or investigational biologics is not allowed until Week 64 even if the subject has discontinued IP. Interaction studies between tezepelumab and other biologics indicated for the treatment of COPD have not been conducted. For additional information regarding pharmacokinetic and pharmacodynamic effects of tezepelumab, please see the Investigator brochure.

All subjects who prematurely discontinue IP should return to the site and complete the procedures described for the premature IP Discontinuation visit (IPD) at 4 weeks (+/-5 days) post last IP administration. Subjects who discontinue treatment should be encouraged to return for all regularly scheduled visits for safety and efficacy assessments.

At the IPD visit the subject will be given three options as to how they will be followed as follows:

- 1. The subject should be encouraged to return for all regular clinic visits and perform all scheduled assessments (excluding IP administration) until the EOT visit at Week 52 (+/-5 days).

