1.3 Number of subjects

Original Sample Size

Approximately 282 subjects will be randomised to either tezepelumab or placebo (1:1) globally from over 80 sites. The subjects will be stratified by region [North America (USA, Canada), Europe (France, Germany, Netherlands, Spain, United Kingdom, Israel, Denmark.), Asia (South Korea)], and prior number of exacerbations (2 vs ≥ 3). Since the primary analysis of the primary endpoint will include all available data, including after treatment discontinuation, no need is envisaged to adjust the number of subjects planned to be randomised to obtain a number of evaluable subjects.

For the primary endpoint of reduction in COPD exacerbation rate, 141 subjects per treatment arm (282 total) will be randomised to achieve 80% power of detecting a 30% reduction in tezepelumab versus placebo over a fixed time period of 52 weeks. This calculation has assumed a one-sided 5% alpha level test, an annual placebo rate of 1.6 events/subject/52 weeks, a negative binomial shape parameter of 0.6, and 10% uniform drop out.

In the absence of the interim analysis for futility, this design would provide 81.2% power, and only 136 subjects per treatment arm would be required for 80% power.

This power statement accounts for the power loss associated with the futility interim analysis that will occur when 182 subjects have been randomised. In simulated results, 1.2% of simulated trials were stopped early for futility but would have been successful at the final analysis of the primary endpoint had they been allowed to continue. Therefore, the overall power for this trial accounting for the interim analysis is 80%. Note that as a result of the pause in recruitment due to COVID-19, the futility analysis is now planned to occur when approximately 30% of follow-up data is available but the expected power loss will be comparable under these conditions.

The primary endpoint will also be tested using a one-sided 2.5% alpha level test, but the sample size has not been determined based on providing power for this test.

Updated Sample Size

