The maximum follow-up time for exacerbations for a subject is approximately 52 weeks; defined under the primary estimand as the time from randomisation to the date of Visit 16 (EOT), regardless of whether subjects remain on randomised treatment. For a subject lost to follow-up or prematurely withdrawing from the study prior to Visit 16 (EOT), this will be defined as the time from randomisation to the time point after which an exacerbation could not be assessed. For subjects who discontinue study treatment and remain in the study after the IPD visit, exacerbations will be counted from the time of randomisation up to and including the date of Visit 16 (EOT). Exacerbations that start after Visit 16 (EOT) will not be included in the efficacy assessments but will be listed. If a subject misses Visit 16 (EOT), then any exacerbations that start after the scheduled Visit 16 (EOT) date will be excluded from efficacy assessments. If an exacerbation is ongoing at Visit 16 (EOT), the exacerbation will be counted in the calculation of annual exacerbation rate, however the maximum follow-up time will be truncated at

the date of Visit 16 (EOT), as will the duration of exacerbation. For the subjects who died during the treatment period the exacerbation data collected up to the date of death will be included in the statistical analysis.

The number of days that the subject experiences an exacerbation during the follow-up time, including the subsequent 7 days (when a further exacerbation would not be considered a separate event (and if within the follow-up time)) will be subtracted from the maximum follow-up time to give the maximum time at risk of exacerbation.

In the primary analysis, the number of COPD exacerbations experienced by a subject during their follow-up time will be used as response variable.

The on-treatment annual exacerbation rate will be calculated similarly, as sensitivity analysis, using exacerbations occurring during the on-treatment period as defined in Section 2.1.5. The same formula for annual exacerbation rate will be used for all the estimands in Section 4.2.4.1, and for the corresponding sensitivity analysis in Appendix 8.2.

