3.2.3.2 Clinically Important Deterioration (CID) event

CID is a composite endpoint measuring worsening of the key clinical features of COPD, namely lung function, subject-reported outcomes, and exacerbations. CID is defined as having met at least one of the following criteria:

- ≥ 100 mL decrease in pre-dose/pre-BD FEV₁ (L) compared to baseline
- Decline in health-related quality of life defined as ≥ 4 unit increase from baseline in SGRQ total score
- Occurrence of a moderate or severe on-treatment COPD exacerbation

Time to CID event will be used as the outcome variable to explore the effect of tezepelumab and it is defined as follows:

Start date of CID event - Date of randomisation + 1

where the start date of the CID event will be the assessment date of any of the three conditions above, whichever occurs first.

Subjects will be evaluated for CID events up to Week 52. The time to CID event for subjects who complete Visit 16 (EOT) and do not experience a CID event will be censored at Visit 16. For subjects lost to follow-up, prematurely withdrawing from the study, or discontinue the study treatment and remain in the study, the time to CID event will be censored at the end of the maximum follow-up time, as described in Section 3.2.1.1.

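### The exploratory EXACT-PRO rate and time to CID use risk time that does not match when their events can be recorded or counted

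*SAP*

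**What the plan says.** **EXACT-PRO rate.** SAP 3.2.3.5 detects an event by comparing daily diary totals with a baseline: a rise of at least 9 points for 3 days, or at least 12 for 2 days. For the summary statistics, the annual rate "will be calculated using the same time-based approach as specified in Section 3.2.1". SAP 4.2.6 then models the rate by the primary method of SAP 4.2.4.1, with log time at risk as the offset. SAP 3.2.1.1 defines maximum follow-up "as the time from randomisation to the date of Visit 16 (EOT), regardless of whether subjects remain on randomised treatment". It ends follow-up sooner only for subjects who are lost or who withdraw from the study.

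**Diary availability.** Protocol 7.1.1 gives subjects who stop IP three follow-up options. Options 1 and 2 keep the eDiary to Week 52. The device is otherwise returned at the EOT visit "and at IPD visit for subjects choosing option 3 below"; option 3 then has a single contact at Week 52.

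**CID.** SAP 3.2.3.2 lists an FEV1 fall, an SGRQ worsening and, third, "Occurrence of a moderate or severe on-treatment COPD exacerbation". SAP 2.1.5 closes the efficacy on-treatment window 33 days after the last dose (or at death or withdrawal, if sooner). The FEV1 and SGRQ components carry no such limit. For subjects who "discontinue the study treatment and remain in the study, the time to CID event will be censored at the end of the maximum follow-up time", SAP 3.2.3.2 points back to SAP 3.2.1.1, which means Visit 16.

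**The concern.** A rate or hazard estimate needs its denominator to cover the time in which an event could enter the numerator. An option 3 subject is neither lost nor withdrawn, so the early cut-off in SAP 3.2.1.1 does not apply. Months without a diary therefore enter the EXACT-PRO offset as event-free time.

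For CID, a subject who stops IP and later exacerbates stays in the Cox risk set with that exacerbation ignored. One composite thus combines an on-treatment component with two components that count whenever they are measured.

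Both endpoints serve stated exploratory objectives. SAP 4.2.6 rules out sensitivity analyses for exploratory endpoints, so no planned re-analysis would show the effect.

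**Working it through.** **1. The plan's own figures.** SAP 1.3 supplies the inputs: "This calculation has assumed a one-sided 5% alpha level test"; the target is "to achieve 80% power of detecting a 30% reduction in tezepelumab versus placebo over a fixed time period of 52 weeks"; and "an annual placebo rate of 1.6 events/subject/52 weeks". Dispersion is 0.6. The 10% uniform drop-out is read as mean follow-up 1 − 0.10/2 = 0.95 year.

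n per arm = (z₀.₉₅ + z₀.₈₀)² × [(1/r₀ + 1/r₁)/t + 2k] / (ln RR)², with r₀ = 1.6, r₁ = 1.12, t = 0.95, k = 0.6:

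- (1.645 + 0.842)² = 6.183
- (0.625 + 0.893)/0.95 + 1.2 = 2.798
- (ln 0.7)² = 0.1272
- n = 6.183 × 2.798 / 0.1272 ≈ 136, as stated.

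Power at 141 per arm is 81.25% (stated 81.2%). At 169 per arm and a placebo rate of 1.2 it is 81.5% before futility loss. None of this involves EXACT-PRO or CID, for which the plan states no figure.

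**2. EXACT-PRO rate.** Assume a share d of an arm stops the diary at a time uniform over the year but is counted to Week 52. The observable fraction of the counted time is then 1 − d/2, and the arm's rate is multiplied by it. The small deduction for event days is ignored.

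- d = 10%: factor 0.95, rate understated by 5%. d = 20%: factor 0.90, understated by 10%.
- Equal d in both arms: the factors cancel and the rate ratio is unchanged. The absolute difference, which SAP 4.2.6 also reports, shrinks. With the primary planning values 1.6 and 0.70 used purely as illustration, −0.48 becomes −0.48 × 0.95 = −0.456 or −0.48 × 0.90 = −0.432.
- Tezepelumab 20%, placebo 10%: 0.90/0.95 = 0.947. A true ratio of 1.00 appears as 0.947 and 0.70 as 0.663.
- Shares reversed: 0.95/0.90 = 1.056. The same true ratios appear as 1.056 and 0.739.

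**3. Time to CID.** Exponential event times were simulated with 400,000 subjects per arm, uniform stop times and a placebo 52-week incidence of 50% or 80%. The SAP rule was taken at its worst: no component of any kind is counted after the stop, and censoring is at Week 52. The comparison censors at the stop. Paired values are for 50% / 80% incidence.

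| Stop share, placebo / tezepelumab | True HR | SAP rule | Censored at stop |
|---|---|---|---|
| 10% / 10% | 1.00 | 0.998 / 1.001 | 0.999 / 1.002 |
| 10% / 20% | 1.00 | 0.945 / 0.944 | 1.001 / 1.003 |
| 20% / 10% | 1.00 | 1.059 / 1.066 | 1.000 / 1.003 |
| 10% / 20% | 0.80 | 0.756 / 0.762 | 0.798 / 0.803 |
| 20% / 10% | 0.80 | 0.855 / 0.859 | 0.804 / 0.802 |
| 20% / 20% | 0.80 | 0.805 / 0.807 | 0.801 / 0.797 |

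With equal stopping, the SAP rule stays within about 0.01 of the hazard ratio from complete data.

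**The case against.** The strongest reply is that little is affected. Both endpoints are exploratory, SAP 4.1.2 makes their p-values nominal, and SAP 4.2.1 already tabulates by arm how many subjects stop IP but remain, by follow-up option. That stands, and it keeps the point modest. The table shows how large the group is but does not correct the estimates.

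Three stronger readings are tempting, and the documents do not support them.

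- *Everyone who stops IP is scored event-free to Week 52.* Options 1 and 2 keep the diary, so EXACT-PRO events remain detectable. For CID, FEV1 and SGRQ events still count where they are assessed: both under option 1, and SGRQ possibly at home under option 2. Events before stopping always count.
- *EXACT-PRO rates are understated by 20% to 30%.* This would take the 8-of-12-days diary criterion in Protocol 5.1 as expected adherence. It is an entry minimum, and compliance is checked at each treatment visit. Scattered missing days need not erase an event lasting several days, and the scoring manual cited in SAP 3.2.3.5, which was not available, may deal with them.
- *The SAP already solved this for COPDCompEx.* SAP 3.2.3.1 mentions the last eDiary assessment, but it clearly shortens follow-up only for subjects who withdraw. It is weak evidence of a rule for those who stay without a diary.

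Also, the on-treatment limit on CID exacerbations is in Protocol 8.1.5, so the SAP did not invent it. The mismatch arises from pairing that limit with censoring at Visit 16.

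**Conclusion.** The point holds within limits. As written, EXACT-PRO risk time includes time without a diary for subjects who remain in the study, chiefly under option 3. The CID risk set keeps subjects whose later exacerbations are ignored.

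The EXACT-PRO rate is understated by about 5% to 10% in an arm where 10% to 20% stop the diary. The rate ratio moves by about 5% to 6% only when stop shares differ by about 10 points. The CID hazard ratio moves by about 5% to 7% under a 10% v 20% imbalance, and by about 0.01 with equal stopping. The CID figures are an upper bound, because they credit no FEV1 or SGRQ event after the stop.

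All sizes rest on assumed stop shares and uniform stop times. The 10% drop-out in SAP 1.3 is a planning figure for the primary endpoint and says nothing about diary use. The primary result, the sample size and the futility rule are untouched.

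**What to change.** **EXACT-PRO (SAP 3.2.3.5 and 4.2.6).** End each subject's follow-up at the earlier of Visit 16 and the last evaluable diary day, define an evaluable day, and use the log of the resulting time at risk as the offset and in the summary rate. The cost is slightly less person-time and an assumption that diary stopping is non-informative.

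**CID (SAP 3.2.3.2).** Align components and censoring in one of two ways.

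- Apply the on-treatment window of SAP 2.1.5 to all three components and censor at its end. This discards off-treatment FEV1 and SGRQ data and assumes that stopping is non-informative. Protocol 8.1.5 puts no such limit on those two components, so the narrowing should also be stated.
- Count every moderate or severe exacerbation to Visit 16, as in the primary estimand. Do not censor earlier at the last clinic assessment: under options 2 and 3, exacerbations are collected by telephone, and earlier censoring would lose them. Record this in SAP Section 6 as a change from Protocol 8.1.5. FEV1 under options 2 and 3, and SGRQ under option 3, would still be unobserved between the IPD visit and Week 52.

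Either route needs only derivation wording and programming on data already collected.

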3.2.3.6 Other subject reported outcome variables

Daily diary metrics collected through Visit 16 (EOT) include rescue medication use, nocturnal awakening, and symptom severity questionnaire.

In the endpoints described in this section, where relevant, one day is defined as the evening measurement followed by the measurement of the following morning.

Total rescue medication use

The number of rescue medication inhalations and nebulizer treatments taken will be recorded by the subject in the eDiary twice daily. Daytime use is recorded in the evening and night-time use is recorded in the morning. Inhaler usage will be reported as the number of puffs in a given period whereas nebulizer use will be reported as the number of times.

The number of inhalations of rescue medication and nebulizer treatments captured in the eDiary each day will be calculated per subject. If a subject is missing a value for either night-time or daytime rescue medication on a given day (evening followed by morning), then the total rescue medication use for that day will be set to missing.

Total rescue medication use (inhaler and/or nebulizer), defined as the number of puffs per day will be calculated as follows:

Number of daytime inhaler puffs (recorded in the evening) + 2 x [number of daytime nebulizer times (recorded in the evening)] + number of night-time inhaler puffs (recorded the next morning) + 2 x [number of night-time nebulizer times (recorded the next morning)]

Total reliever inhaler puffs per day will be calculated as:

Number of daytime inhaler puffs (recorded in the evening) + number of night-time inhaler puffs (recorded the next morning)

Total nebulizer use (number of times) per day will be calculated as:

Number of daytime nebulizer times (recorded in the evening) + number of night-time nebulizer times (recorded in the next morning)

Biweekly mean rescue medication use (average puffs/day in total use) and change from baseline in the biweekly mean rescue medication use will be calculated.

Night awakenings

Subjects will be asked to report the occurrence of nocturnal awakenings due to COPD symptoms each morning using the electronic patient reported outcome (ePRO) device. A single question with yes/no response options will be used.

The biweekly proportion of nights with nocturnal awakenings due to COPD symptoms with non-missing night-time awakening data, and the corresponding change from baseline for each post-randomisation period will be calculated.

3.2.3.7 Healthcare resource utilisation due to COPD

COPD related healthcare resource utilisation information will be collected by the Investigator/authorized delegate at each visit as specified in the protocol and recorded in the appropriate eCRF module.

The number of days/times the following resources were utilised and the corresponding annual rates through Visit 16 (EOT) will be presented for each subject:

- Ambulance transport
- Hospitalisation, intensive care (days in intensive care)
- Hospitalisation, general care (days in general care)
- Emergency room visit (24 hrs) or urgent care
- Visit to specialist
- Visit to primary health care physician
- Other health care visit
- Home visit, physician

- Home visit, other health care
- Telephone call to physician
- Telephone call to nurse
- Telephone contact with other/health care provider

If multiple healthcare encounters are associated with one COPD exacerbation, all the encounters will be counted for this endpoint.

The annual rate of each resource utilisation through Visit 16 (EOT) will be calculated according to the formula described below:

*Annual rate of resource utilisation = Number of times * 365.2 / (Last follow-up date – Visit 3 date + 1)*

